8.2 Research Ethics Committee (REC) and other Regulatory review & reports

Before the start of the study, a favourable opinion will be sought from an NHS Research Ethics Committee (REC) for the study protocol, informed consent forms and other relevant documents associated with this protocol.

- Any amendments, with the agreement of the sponsor, will be submitted to the relevant regulatory body. Substantial amendments that require review by NHS REC will not be implemented until that review is in place and other mechanisms are in place to implement at site.
- All correspondence with the REC will be retained.
- The Chief Investigator will produce annual reports as required.
- The Chief Investigator will notify the REC of the end of the study.
- An annual progress report (APR) will be submitted to the REC within 30 days of the anniversary date on which the favourable opinion was given, and annually until the study is declared ended.
- If the study is ended prematurely, the Chief Investigator will notify the REC, including the reasons for the premature termination.
- Within one year after the end of the study, the Chief Investigator will submit a final report with the results, including any publications/abstracts, to the REC.

Regulatory Review & Compliance

- Before any site can approach participants about the study, the Chief Investigator/Principal Investigator will ensure the study has gained HRA approval and REC favourable opinion.
- For any amendment to the study, the Chief Investigator in agreement with the sponsor will submit information to the HRA and REC for them to issue approval for the amendment. The Chief Investigator will work with sites (relevant R&D departments) so they can put the necessary arrangements in place to implement the amendment to confirm their support for the study.

Amendments

The Project Management Team in collaboration with the Sponsor will determine whether an amendment is substantial or non-substantial. The guidance below will be followed: https://www.hra.nhs.uk/approvals-amendments/amendments/amendments/amendments/

Following the decision, the Study Co-ordinator will amend the protocol and any associated documents and will notify the REC following the process described in the REC's initial decision letter/the Amendment Tool.

Version numbers and dates on documents will be used to identify the most recent protocol and documents. A separate document listing all amendments with dates and version numbers will be used to facilitate the process.

8.3 Safety Reporting

In the unlikely event that any Serious Adverse Events (SAEs) related to the intervention or research procedures should occur, the CI is responsible for ensuring that all staff involved in this study are familiar with the content of this section. Cis are responsible for notifying the Study Co-ordinator and CI. All SAEs must be reported immediately (and within 24 hours of knowledge of the event) to the sponsor by the study team. SAEs will be assessed at all follow-up time points, and intervention delivery staff will be trained to report these directly to the study team at any point during the study. Rates of SAEs by study arm will be reported to the TSC, and if required, to the REC. Additional information about the potential harm of the intervention will be collected through qualitative interviews with all stakeholders.

8.3.1 Definitions

Term	Definition
Adverse Event (AE)	Any untoward medical occurrence in a participant administered an intervention which are not necessarily caused by or related to the VIG.
Serious Adverse Event (SAE)	 Any adverse event that - Results in death Is life-threatening* Required hospitalisation or prolongation of existing hospitalisation** Results in persistent or significant disability or incapacity Consists of a congenital anomaly or birth defect Other medically important condition***

^{*}Note: The term 'life-threatening' in the definition of serious refers to an event in which the study participant was at risk of death at the time of the event or it is suspected that used or continued used of the product would result in the participants death; it does not refer to an event which hypothetically might have caused death if it were more severe.

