2. RATIONALE	
3. THEORETICAL FRAMEWORK	
4. RESEARCH QUESTION/AIM(S)	
5. STUDY DESIGN/METHODS	
6. STUDY SETTING	
7. SAMPLE AND RECRUITMENT	
8. ETHICAL AND REGULATORY COMPLIANCE	
9. DISSEMINATION POLICY	
10. REFERENCES	
11. APPENDICES	

KEY STUDY CONTACTS

Insert full details of the key study contacts including the following

Chief Investigator	[name]	
	[contact]	
	[name]	
Study Co-ordinator	[name]	
	[contact]	
Sponsor	Tavistock and Portman NHS Foundation Trust, Research and Development, Noclor Research Support Service, [name]	
	E: [contact]	
	T: [name]	
Joint-sponsor(s)/co-sponsor(s)	N/A	
Funder(s)	NIHR Research for Patient Benefit (RfPB) [name].	
	Reference NIHR 203051	
Key Protocol Contributors	[name] ([contact])	
	[name] ([contact])	
	[name] ([contact])	
	[name] ([contact])	
	[name] ([contact])	
	[name] [name] ([contact])	
	[name] ([contact])	
	[name] ([contact])	
	[name] ([contact])	
Committees	Project Management Group (PMG): led by [name], includes all co-investigators (see above) plus Study Co-ordinator	
	Contact: [contact]	
	Trial Steering Committee (TSC): chaired by [name] ([contact]; Child and Adolescent Psychiatrist). Members: [name] (Statistician), [name] (Paediatrician) and [name] (Parent Expert)	

Parent/Carer Advisory Group (PCA): led by [name] ([contact]), PPI lead. The PCA
includes 10 parent/carers of children with a learning disability.

STUDY SUMMARY

Study Title	A feasibility trial of remotely-delivered Video Interaction Guidance [VIG] for families of children with a learning disability referred to specialist mental health services
Internal ref. no. (or short title)	VIG-LD
Study Design	Feasibility RCT with embedded process evaluation and a parallel feasibility economic evaluation
Study Participants	Parents who have a 6-12 year old child with a learning disability who has been referred to specialist mental health services
Planned Size of Sample (if applicable)	N=50
Follow up duration (if applicable)	6 months
Planned Study Period	July 1 st 2022 – December 31 st 2024
Research Question/Aim(s)	Research objective: To determine the feasibility of a randomised controlled trial evaluation of remotely delivered Video Interaction Guidance (VIG) to parents of children with LD referred to specialist child mental health services.

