Children with LD with challenging behaviour or mental health problems are referred to specialist child mental health services for treatment and support. Specialist mental health services are increasingly under strain (NHS Digital, 2020a), with therapy waiting time approaching 12 months; these issues have been exacerbated due to the pandemic. Remote family interventions could be an effective solution for both families and specialist mental health services (Aref-Adib & [name], 2021). The NHS long-term plan proposes digital interventions should be adopted to ease the pressure on specialist child mental health services. The Children's Commissioner (Children's Commissioner for England Office, 2021) highlights that, post-pandemic, remote interventions are even more crucial for achieving the NHS long-term plan. Where staff have had the experience of remote interventions (during the

pandemic), they are keen to adopt them as a regular service offer, because they could improve access, waiting times and non-attendance rates (Sheehan et al., 2021).

Why is this research important?

Challenging behaviours and mental health problems in children with LD can lead to family breakdown and children have to move to specialist residential schools or inpatient units. Seventy per cent of about 6,000 children in residential schools are there because of challenging behaviour (Lenehan & Gerachty, 2017). Such placements cost up to £500m a year (Lenehan & Gerachty, 2017). A placement in Assessment and Treatment Units (ATUs) is estimated at £5m over three years per child (Lenehan, 2017). There are 250 children in ATUs (NHS Digital, 2020b). Parents say 'there is a better way' to support these children and families.

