Participants will be asked to complete and send the signed consent within 24 hours of the meeting (if it is a working day). Participants will be asked to volunteer reasons for not consenting to participation if they choose. If the consent form is not received, the VIG-LD researcher will contact the potential participant three more times spread over a three week period. If a potential participant does not respond following the 3rd attempt they will not be contacted again.

As the parent is the participant in the present study, child assent will not be sought. However, consenting and eligible parents will be provided with a Child Notification Letter that explains the purpose and process of the study to children. The participant will be encouraged to go through the Child Notification Letter with their child. The letter includes information on how to contact the Study Coordinator if the child wishes to do so.

A separate consent form will be obtained for those who will participate in the process evaluation interviews; these will be both clinical service staff and parents. For this part of the study, a separate Participant Information Sheet and Consent form are available

Due to the aims and context of the research, monitoring of participants' capacity will not be undertaken. After consent, continued capacity will be assumed. However, help resources will be available through their clinical team should a participant require support due to loss of capacity.

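### As worded, the SAE definition leaves out the index child, and its limit to people given an intervention contradicts the by-arm and from-consent reporting rules

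*Protocol*

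**What the plan says.** Protocol section 8.3.1 defines an adverse event as "Any untoward medical occurrence in a participant administered an intervention", and the same sentence adds that the event need not be due to VIG. The SAE definition beneath it opens with "Any adverse event that" and then lists the seriousness criteria. The note on life-threatening events describes "an event in which the study participant was at risk of death at the time of the event".

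The study summary describes the study participants as "Parents who have a 6-12 year old child with a learning disability who has been referred to specialist mental health services". Section 7.3.2 is explicit: "As the parent is the participant in the present study, child assent will not be sought".

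On reporting, section 8.3 requires SAEs to reach the sponsor within 24 hours, to be assessed at every follow-up, and to be summarised by arm: "Rates of SAEs by study arm will be reported to the TSC, and if required, to the REC". Section 8.3.2 gives the chief investigator the causality grading. Section 8.3.4 starts SAE reporting when consent is signed.

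**The concern.** The person named in the safety definition is not the person whose health the trial is chiefly about. The child is the patient referred to the mental health service (section 7.1.1) and is filmed with the parent in VIG (section 4.3). The child's DBC2 score is the likely primary outcome of a full trial (section 5, study retention). Among the bad outcomes that section 1 describes for these families is that "children have to move to specialist residential schools or inpatient units". If staff follow the definition as written, a serious medical event in the child does not enter SAE reporting.

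A second difficulty lies in the same sentence. It limits events to people who have been administered an intervention, while other parts of the safety section assume that events are counted in both arms and from consent. The definition and the reporting rules cannot both be followed literally.

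**Working it through.** The plan gives no event rate or other figure to reproduce here. The check sets the passages side by side and ends with a head count.

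**1. Whose events can be SAEs.** An SAE must first be an adverse event, so the population limit in the adverse-event definition carries into every SAE. The second half of that sentence, on relatedness to VIG, removes any causality requirement but adds no one to the population. The notes on life-threatening and other medically important events again speak only of the participant. Nothing in section 8.3 mentions the child.

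**2. Who the participant is.** The study summary, section 7.1 and section 7.3.2 all say the parent. Section 7.3.2 relies on that meaning to justify not seeking the child's assent, so it is hard to read the child back into the same word in section 8.3.1.

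**3. What follows for the child.** A child's death, life-threatening event or unplanned admission would meet a listed seriousness criterion but fail the population condition. It is then not an SAE, and the 24-hour report, the causality grading and the by-arm TSC rates do not apply to it.

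**4. Whether another route closes the gap.**
- Qualitative harm interviews (section 8.3): section 5 plans about 10 parents and about eight clinical staff, at 6 months. These yield no SAE report and no rate.
- Safeguarding escalation (section 8.1): triggered by disclosures with safeguarding implications, and separate from SAE reporting.
- CA-SUS service-use interview (section 5): at baseline and 6 months. It may record a child's admission, but nothing sends that entry to the SAE form.

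**5. Arm and start time.** Section 5 contrasts intervention with treatment as usual (TAU), and section 6 contrasts the intervention group with the comparison group. On that usage, a person administered an intervention is a VIG-arm parent.

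| Rule | Where | Fit with section 8.3.1 on that usage |
|---|---|---|
| SAE rates given for each arm | 8.3 | The TAU arm could have no SAEs by definition |
| SAEs reported from consent | 8.3.4 | Consent precedes randomisation (section 5), when nobody has yet received VIG |

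Section 4.3, however, uses intervention loosely enough to include other elements of usual support, so the word is not used consistently.

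**6. Head count.** Inputs: 50 parents (section 5) and one index child per parent. The second is an assumption, consistent with the exclusion of families in which another sibling takes part (section 7.1.2). Index children = 50 × 1 = 50. Children covered by the stated definition = 0 of 50. This shows whom the words reach. It is not an estimate of missed events.

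**The case against.** The strongest reply is that section 8.3 is generic text that was not adapted to this trial, and not a decision to exclude children. It refers to a product, and section 8.3.2 grades causality against the participant's clinical condition, which suits the referred child at least as well as the parent. The data-protection text in sections 5 and 8.7 illustrates a participant with rare characteristics by describing a child. Delivery staff are trained to report SAEs to the study team at any time, and some may report child events regardless. This stands as a limit on certainty: it cannot be said that a child event could never be reported, or that the TSC would see no child harm whatever happened. It does not repair the definition, because the only explicit statement of who the participant is names the parent.

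A reader might also infer that TAU events will go uncounted, so that only the 25 VIG-arm parents (50 ÷ 2) among 100 parents and children are covered. The documents do not support this. By-arm reporting, the start at consent, and the contrast in the definition between an unspecified intervention and VIG itself all point to both arms being intended.

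Nor should the gap be tied to the progression decision. The criteria in section 5 concern recruitment, retention, VIG completion and measure completeness, and none uses SAE rates. Finally, a move to a residential school is not in itself an inpatient admission, so not every outcome described in section 1 would become an SAE under better wording.

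**Conclusion.** The point holds in two parts of different strength. The first is firm on the text: as defined, serious events in the index child are outside SAE reporting (0 of 50 children, assuming one per parent and full recruitment), and no other route in the protocol feeds them to the sponsor report, the causality grading or the by-arm rates. How many events this would miss cannot be stated, because the protocol gives no rate.

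The second part is an internal contradiction: the adverse-event definition, read with the usage in sections 5 and 6, conflicts with by-arm reporting in section 8.3 and with the start at consent in section 8.3.4. It needs reconciling and is not evidence that TAU events will be lost.

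What is at stake is the completeness of safety oversight during the trial, not the feasibility conclusions. Whose events count is fixed in the protocol's own safety section, so this is not a detail left to the analysis plan.

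**What to change.** Reword section 8.3.1 so that an adverse event is an untoward medical occurrence in the participating parent or the index child, in either study arm, from signed consent onward, whether or not related to VIG. Adjust the notes on seriousness and the causality descriptions so that they refer to the affected person. In section 8.3, state that SAE rates go to the TSC by arm, separately for parent and child. The report form is not shown; if it does not already record who was affected, it should.

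The cost is a short protocol amendment, possibly one form field, and some additional SAE reports, since admissions of these children would now be captured. The progression criteria need no change.

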8.3.2 Causality

The assessment of whether or not an SAE is a consequence of receiving the intervention will be provided by the CI.

Relationship	Description	Reasonable possibility that the SAE may have been caused by the intervention?
Unrelated	There is no evidence of any causal relationship with the intervention	No
Unlikely	There is little evidence to suggest there is a causal relationship with the intervention. There is another reasonable explanation for the event (e.g. the participant's clinical condition, other concomitant treatment).	No
Possible	There is some evidence to suggest a causal relationship with the intervention. However, the influence of other factors may have contributed to the event (e.g. the participant's clinical condition, other concomitant treatments).	Yes
Probable	There is evidence to suggest a causal relationship and the influence of other factors is unlikely.	Yes
Definite	There is clear evidence to suggest a causal relationship and other possible contributing factors can be ruled out.	Yes

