8 ETHICAL AND REGULATORY CONSIDERATIONS

8.1 Assessment and management of risk

There are three potential risks to participants in this study:

- 1) The protection of their personal information and the provision of informed consent for participation: participants will be provided with clear information on the mechanisms associated with the protection of their personal information in the Participant Information Sheet. Participants need to provide written informed consent to participate in the present study. A Data Management Plan will be developed to guide all aspects of data management and data analysis prior to data collection.
- 2) Psychological distress during data collection: as participants will be invited to provide information about their child's behaviours that challenge and mental health, it is likely they might experience mild psychological distress associated with reflecting on their own mental health and the challenging behaviours of their child while filling in the relevant questionnaires. The Participant Information Sheet alerts participants to this risk and directs them to resources and support available by the charity Cerebra (that is independent of this study) as well as to their GP or collaborating clinical sites teams. The study team have developed a letter addressed to the GP informing of the nature of the study and what participation involves. Parents are provided with a copy of this letter once their participation is confirmed and have the choice to share with their own GP as desired.
- 3) Disclosure of issues that have safeguarding implications during data collection processes: data collection involves interviews with participants. In the event of disclosure of an issue that has safeguarding implications (adult safeguarding or child safeguarding), the researcher will raise the issue with their line manager (both the study CI and [name]) immediately following the disclosure and no later than 24 hours after the disclosure. Trust policy will be followed should the matter need to be escalated further by contacting [contact]

Potential risks to researchers in this study:

There is minimal risk to the researchers themselves as all research will be done remotely. Researchers will be offered supervision and are able to contact the CI after data collection

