8.3.4 Reporting procedures

Any queries concerning adverse event reporting should be directed to the Study Co-ordinator.

All SAEs, whether expected or not, should be recorded on the relevant report form and followed up to resolution wherever possible. The CI (or delegated member of the SMG) should sign and date the SAE reporting form to acknowledge that they have performed the seriousness and causality assessments. SAEs should be reported from time of signature of informed consent, throughout the treatment period.

An SAE form is not considered as complete unless the following details are provided:

^{**} Note: Hospitalisation is defined as an inpatient admission, regardless of the length of stay, even if the hospitalisation is a precautionary measure for continued observation. Pre-planned hospitalisation e.g. for pre-existing conditions which have not worsened, or elective procedures, does not constitute an SAE.

^{***} Note: other events that may not result in death, are not life-threatening, or do not require hospitalisation, may be considered as an SAE when, based upon appropriate medical judgement, the event may jeopardise the participant and may require medical or surgical intervention to prevent one of the outcomes listed above.

- Full participant study number
- A Serious Adverse Event
- A completed assessment of the seriousness, and causality as performed by the CI (or another appropriately qualified individual on the delegation log).
- Only reports of related and unexpected SAEs should be submitted to the REC. These should be sent within 15 days of the CI becoming aware of the event.

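### SAE causality is assessed only against VIG, although section 8.3 also covers research procedures, so an SAE caused by a procedure would be graded not related and miss the individual REC report

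*Protocol*

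**What the plan says.** Section 8.3 of the protocol opens with the case that "any Serious Adverse Events (SAEs) related to the intervention or research procedures should occur", so two sources of harm are in view: VIG and the research itself.

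Section 8.3.2 gives the only causality rule: "The assessment of whether or not an SAE is a consequence of receiving the intervention will be provided by the CI". The decision column of its table is headed "Reasonable possibility that the SAE may have been caused by the intervention", and the lowest grade, Unrelated, is defined as "There is no evidence of any causal relationship with the intervention". The Unlikely and Possible rows also name the intervention. The Probable and Definite rows speak only of a causal relationship, but they sit under the same column heading and the same lead sentence.

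Section 8.3.4 then states: "Only reports of related and unexpected SAEs should be submitted to the REC", within 15 days of the CI learning of the event. It does not say what related means. It starts SAE reporting at signature of consent, and it treats an SAE form as incomplete without a causality assessment. Section 8.3.1, by contrast, defines an adverse event as something that happens to a participant who has been given an intervention.

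**The concern.** The scope statement covers two causes and the grading instrument covers one. An SAE brought about by a screening call, a questionnaire or an interview has no causal link with VIG, so the scale steers the assessor to a No answer. The REC rule depends on that answer.

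This matters more here than in most trials because of where the protocol locates risk. Section 8.1 says "There are three potential risks to participants in this study". The first is "The protection of their personal information and the provision of informed consent for participation". The other two are psychological distress and safeguarding disclosures, both arising during data collection. All three come from taking part in the research, and none is attributed to VIG. The causality question therefore leaves out the only source of risk that the protocol names. A report that no related SAE occurred could be literally correct and still say nothing about harm from study procedures.

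**Working it through.** The protocol states no figure on this point that could be reproduced, so the check sets the sections side by side and follows one event through them.

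1. **Scope (8.3).** Intervention or research procedures.
2. **Causality question (8.3.2, lead sentence and column heading).** Intervention only. No second grading for research procedures appears anywhere in section 8.3.
3. **REC rule (8.3.4).** Related and unexpected only. Since related is not defined there, the grade from 8.3.2 is the only relatedness assessment on the form.
4. **When each cause can act.** Consent is signed before any data collection, including screening (7.3.2). Eligibility screening with the Vineland interview, the baseline questionnaires and the service-use interview all come before randomisation (section 5, Appendix 2). SAE reporting starts at consent (8.3.4). So every participant passes through a reporting period in which VIG cannot be a cause and research procedures can.
5. **Who never receives VIG.** The design is 50 parents allocated 1:1 (section 5): 50 / 2 = 25, so about 25 parents are in the TAU arm. They complete the same participant questionnaires and interviews as the VIG arm and do not receive VIG.
6. **One event traced.** Suppose a parent is admitted in crisis and the assessor judges that the baseline interview brought it on.
   - Scope in 8.3: inside.
   - Grade in 8.3.2: there is no evidence of a link with VIG, so the grade is Unrelated. The column reads No.
   - REC rule in 8.3.4: not related, so there is no 15-day individual report.
7. **Same event in the VIG arm.** If the cause is the procedure alone, the grade is Unrelated or at most Unlikely. Both read No, so the result is the same.
8. **What still happens to the event.** It goes to the sponsor within 24 hours (8.3). It is recorded and followed up (8.3.4). It counts in the SAE rates by arm that go to the TSC and, if required, to the REC (8.3). None of these routes records that a research procedure caused it.
9. **Adverse event definition.** Section 8.3.1 ties an adverse event to a participant given an intervention, and an SAE is defined there as a kind of adverse event. Taken literally, an event between consent and randomisation is not an adverse event at all, which conflicts with the start of reporting in 8.3.4.

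**The case against.** The strongest objection is that 8.3.4 does not tie related to the table in 8.3.2. The only sentence that says what SAEs may be related to is the opening of 8.3, and it includes research procedures. On that reading a CI could send a procedure-related SAE to the REC without breaching the protocol. This stands in part: the text does not forbid such a report. But the form needs a causality assessment, and the only scale supplied has nowhere to record a procedure as the cause.

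A second objection is that the risks in 8.1 would seldom be SAEs. The distress is described as mild, and section 8.1 handles all three risks by other means, such as signposting and safeguarding escalation. This stands. The gap concerns the uncommon case in which distress escalates to, for example, an admission.

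Three stronger readings are tempting and are not supported.

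- A reader might infer that procedure-related SAEs never reach the REC, or that its oversight of study procedures is empty. Rates by arm may go to the REC if required, and section 8.2 provides for annual and final reports. Only the individual report is at risk.
- A reader might count all consenting parents who never receive VIG as affected. The number is not fixed: section 5 describes 100 families as eligible in one place and about 100 as consenting in another, with 97 to be approached. Whether parents who are never randomised fall under SAE reporting is itself unclear, given the conflict between 8.3.1 and 8.3.4.
- A reader might use an event after the 6-month interview as the example. That depends on a separate question, because 8.3.4 runs reporting through the treatment period while 8.3 assesses SAEs at all follow-up points. Events after screening or baseline show the gap without it.

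**Conclusion.** The point holds as an internal contradiction in which a stated rule gives the wrong classification. Read literally, section 8.3.2 grades an SAE caused by a research procedure as not related, and 8.3.4 then withholds the 15-day individual REC report. This reaches every participant between consent and randomisation, and about 25 of 50 parents in the TAU arm while SAEs are being reported. It also reaches the VIG arm where the procedure alone is the cause.

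The size in events cannot be given. The protocol states no SAE rate and regards related SAEs as unlikely. Sponsor notification and aggregate reporting are unaffected, and no feasibility outcome or progression criterion changes. The conclusion assumes that the 8.3.2 grade is what decides related in 8.3.4, which is the natural reading because no other relatedness assessment is provided. It should be corrected, as a matter of consistent safety reporting.

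**What to change.** - **Section 8.3.2:** change the lead sentence, the column heading and the table rows so that causality is assessed against the intervention or research procedures, in both arms and from consent. Record which of the two is implicated. Two fully separate grades are one way to do this; a combined question with a tick for the source would also reconcile the text.
- **Section 8.3.4:** define related as possible, probable or definite for either source.
- **Section 8.3.1:** reconcile the adverse event definition with reporting from consent, so that it also covers TAU parents and participants not yet randomised.

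The cost is wording in three short sections and one line on the SAE form, submitted as a protocol amendment. No extra visits, data collection or staff are needed.
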